#### **I.Objectives**

The goal of this study is to apply a social-network approach to investigate the effects of a peer-mediated intervention to improve socialization processes in preschool inclusive classrooms for children with language impairment, as a mechanism for improving interactions with peers, exposure to peer talk, and children's social, behavioral, and linguistic skills.

#### **II.Background and Rationale**

Language impairment (LI) is a high-incidence developmental disability that significantly elevates a child's susceptibility for peer maltreatment, including exclusion from peer social networks and victimization by peers. Studies find, for instance, that nearly 40% of preschoolers with LI are excluded from their classroom social network (Justice, Chen, Jiang, Tambyraja, & Logan, 2019) and a similar percentage of primary-grade pupils with LI are regularly victimized by their peers (Conti-Ramsden & Botting, 2004). These circumstances reflect in part the relatively poor social competence and pragmatic-language skills of children with LI (Longobardi, Spataro, Frigerio, & Rescorla, 2016), but also the socialization processes that characterize classroom settings. Specifically, as early as the preschool years, children demonstrate strong homophilic behaviors in establishing peer relationships in their classrooms (Chen, Lin, Justice, & Sawyer, 2019), preferring to play with others of the same gender, age, skill levels, and disability status. In preschool settings, children with LI tend to interact most frequently with other children with LI, even in inclusive settings serving children with disabilities and typically developing peers (Justice, Chen, et al., 2019).

The social difficulties experienced by children with LI, particularly social exclusion, can lead to numerous adversities in the short and longer term; this includes school avoidance and disliking, dis-engagement in classroom learning activities, academic under-achievement, and escalating externalizing behaviors (Buhs & Ladd, 2001; Bulotsky-Shearer et al., 2012; Fantuzzo, Sekino, & Cohen, 2004; Nakamoto & Schwartz, 2010). Peer maltreatment via social exclusion also inhibits the opportunity for children with LI to interact with peers with more sophisticated language skills, representing a key mechanism for improving the language skills of children with LI in inclusive classroom settings via well-documented 'peer effects' (Justice, Logan, Lin, & Kaderavek, 2014a). Peer effects is the phenomenon in which children's language growth is positively linked to their classmates' level of linguistic ability (Justice et al., 2014a). Peer effects have been measured by comparing the performance of individual students to the aggregated score of the group to examine effects on literacy, self-regulation, and development (Chen et al., 2019). These methods may capture a global overview of interactions, but are limited in capturing the more in-depth experiences of individual children and their teachers. The mechanism by which those peer effects work is not typically measured.

In the proposed study, we apply a social-network approach to investigate the effects of a peer-mediated intervention to improve socialization processes in preschool inclusive classrooms for children with LI, as a mechanism for improving interactions with peers, exposure to peer talk, and children's social, behavioral, and linguistic skills. We build upon a large body of work showing the positive effects of peer-mediated interventions, especially for children with autism spectrum disorder, but innovate further by (1) studying this approach for children with LI, (2) applying advanced technologies from computer engineering to rigorously explore social processes for children with LI targeted by the intervention, and (3) using social network indices in addition to child-level outcomes to assess intervention effects.

The specific goals for this study are:

1. To determine the extent to which peer-mediated pivotal response training yields direct effects on peer social interactions for children with LI in the classrooms social network.
2. To determine the extent to which peer-mediated pivotal response training yields indirect (mediated) effects on the social, behavioral, and linguistic skills of children with LI
3. To determine the extent to which peer-mediated pivotal response training targeting focal children may broadly effect the social network dynamics at the classroom level.

### **III. Procedures**

#### **a. Research Design**

In order to validate the technology, the research team will conduct a small pilot in the summer of 2021 in two central Ohio classrooms. The goal of this small pilot is to ensure the accuracy, validity, and feasibility of technology and observation instruments that will be used in the large study overviewed below. This pilot study involves 2 inclusive preschool classrooms and an estimated 40 3- to 5- year-old children from these classroom, comprising approximately 25 children with disabilities and 15 typically developing peers. Sample estimates are based on the same calculations used in the larger study that are overviewed in the paragraph below. The same classroom eligibility criteria will be used for the pilot as the larger study (i.e., an eligible classroom must serve  $\geq 3$  children with educational determination of LI per a certified speech-language pathologist). The study team will use the same method to establish focal children and peers as the larger study overviewed below (Focal children ( $n = 1$  per classroom): First, we identify all children's positions within the classroom social network using a teacher matrix (TRPI) conducted in summer 2021; from this network we calculate a child-level social network index (i.e., individual degree centrality; lower scores are characteristic of social exclusion (Justice, Chen, et al., 2019)). Second, teachers simultaneously complete the Developmental Pragmatic Profile (DPP) (Wiig, Secord, & Semel, 2004) for each child in the classroom. This is a 26-item psychometrically sound checklist assessing children's pragmatic skills (e.g., conversational abilities, giving information), and DPP scores have strong classification accuracy in differentiating children with LI from non-affected classmates (Justice, Ahn, & Logan, 2019). Third, teachers also use a checklist to identify children with LI in each classroom per four criteria: the child (1) is on the caseload of a speech-language pathologist, (2) has no known additional diagnoses causal of LI, such as ASD, (3) primarily communicates in English, and (4)

is greater or equal than 42 months of age. Finally, among the children with LI, we select the target child based on the lowest centrality scored weighted by DPP score, so that focal children represent the most socially isolated children with the poorest social-pragmatic communication skills.

The two classrooms/teachers participating in the pilot will complete a 6 week suite of activities to include: trainings, three storybook readings and corresponding peer mediated strategy facilitations during weeks (e.g., Monday, Wednesday, Friday), observation of facilitation sessions by research staff

The main study involves 90 inclusive preschool classrooms/90 teachers and an estimated 900 3- to 5-year-old children from these classrooms, comprising approximately 770 children (approximately 423 of which have diagnosed disabilities) and 770 parents (N=1630). Sample estimates are based on Ohio's inclusive model of preschool special education and our prior work in these settings, in which 55% of students have disabilities (Justice, Logan, Lin, & Kaderavek, 2014b). For the proposed study, an eligible classroom must serve  $\geq 3$  children with educational determination of LI per a certified speech-language pathologist.

The study uses a wait-list **experimental design** to estimate treatment impacts, with 30 Ohio classrooms assigned to the treatment condition and 20 to the control condition. All remaining 40 classrooms will be recruited by our partners at external sites and serve control condition classrooms. Within each classroom, the focal participants are 30 children with LI, one selected per classroom using a priori exclusionary and inclusionary criteria. The wait-list design allows eligible children with LI in control classrooms to receive treatment in the spring semester; this also allows for ongoing evaluation of changes in socialization processes in treatment classrooms through spring. Study methods with OSU classrooms use a sequential cohort design, with 15 classrooms participating in each of two consecutive years to disperse study activities over a 24-month period. Classrooms will be recruited via our extensive network of affiliated preschool programs across the state of Ohio, with eligible classrooms utilizing a 50/50 inclusive service delivery model (50% of children with disabilities). In the fall of each year, once all 15 classrooms are recruited, simple random assignment will be used to allocate 10 classrooms to the treatment group and 5 to the control group, with the latter implementing intervention in spring per the wait-list design. In addition, our colleagues at the University of Kansas, are employing similar observation methods. We will thus incorporate 20 classrooms (University of Kansas) to serve as control condition classrooms, allowing for a more robust sample of natural conditions in preschool classrooms across contexts.

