### **b. Sample**

This study examines the socialization experiences of preschool children with LI inclusive classrooms and the entire classroom social network. Thus, we seek to consent all children in each classroom as participants in this study. For children who are not focal children or peers assisting with the intervention, we will seek caregiver consent to observe their children in the classroom and for caregivers to complete a simple questionnaire about their children. We typically are able to actively or passively consent 90% of children in a classroom.

Focal children (n = 30). We describe inclusionary and exclusionary criteria for the 30 focal children with LI. First, we identify all children's positions (n = 495) within the classroom social network using a teacher matrix conducted in fall of the academic year; from this network we calculate a child-level social network index (i.e., individual degree centrality; lower scores are characteristic of social exclusion (Justice, Chen, et al., 2019)). Second, teachers simultaneously complete the Developmental Pragmatic Profile (DPP) (Wiig, Secord, & Semel, 2004) for each child in the classroom. This is a 26-item psychometrically sound checklist assessing children's pragmatic skills (e.g., conversational abilities, giving information), and DPP scores have strong classification accuracy in differentiating children with LI from non-affected classmates (Justice, Ahn, & Logan, 2019). Third, teachers also use a checklist to identify children with LI in each classroom per four criteria: the child (1) is on the caseload of a speech-language pathologist, (2) has no known additional diagnoses causal of LI, such as ASD, (3) primarily communicates in English, and (4) is greater or equal than 42 months of age. Finally, among the children with LI, we select the target child based on the lowest centrality scored weighted by DPP score, so that focal children represent the most socially isolated children with the poorest social-pragmatic communication skills.

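### Research Design states 30 treatment and 20 control Ohio classrooms, but the random assignment it describes delivers 20 and 10

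*Combined protocol and SAP*

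**What the plan says.** All the allocation figures are in section III.a, Research Design; section III.b, Sample, repeats the focal-child count.

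- Stated Ohio allocation: "with 30 Ohio classrooms assigned to the treatment condition and 20 to the control condition".
- External classrooms: "All remaining 40 classrooms will be recruited by our partners at external sites and serve control condition classrooms".
- Cohorts for the Ohio (OSU) classrooms: "with 15 classrooms participating in each of two consecutive years".
- Randomisation each fall, once the 15 are recruited: "simple random assignment will be used to allocate 10 classrooms to the treatment group and 5 to the control group". The five controls start the intervention in spring.
- Kansas: "We will thus incorporate 20 classrooms (University of Kansas) to serve as control condition classrooms".
- Focal children: "the focal participants are 30 children with LI, one selected per classroom". Section III.b agrees: "We describe inclusionary and exclusionary criteria for the 30 focal children with LI".
- Total: "The main study involves 90 inclusive preschool classrooms/90 teachers".

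All of this is current text. No redaction, broken table or amendment log accounts for the differences.

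**The concern.** The Ohio classrooms supply the only randomised comparison in the study. The external classrooms are controls and are not part of the described random assignment. The sentence that introduces the design gives one pair of arm sizes, and the sentence that says how classrooms are allocated implies another. The ratios differ as well as the totals, so rounding or a uniform change of scale does not explain the gap.

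Two practical things are at stake. The size of the randomised comparison would be misreported if it were taken from the introductory sentence. Recruiting staff also have no consistent target for the number of Ohio classrooms.

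**Working it through.** **Inputs** (section III.a unless noted): stated Ohio arms 30 and 20; 15 classrooms per cohort; 2 cohorts; 10 to treatment and 5 to control per cohort; 40 external classrooms; 20 Kansas classrooms; 90 classrooms in all; 30 focal children, one per classroom (also III.b).

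**1. The plan's own figures.** Stated Ohio total: 30 + 20 = 50, ratio 30/20 = 1.5. Adding the external classrooms, 50 + 40 = 90, which reproduces the stated total if Kansas is counted within the 40.

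**2. The described randomisation.** Classrooms per arm = cohorts × classrooms per arm per cohort.

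- Treatment: 2 × 10 = 20
- Wait-list control: 2 × 5 = 10
- Ohio total: 2 × 15 = 30, which agrees with 20 + 10
- Ratio: 20/10 = 2

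**3. The gap.**

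| | Stated | From the procedure | Difference |
|---|---|---|---|
| Treatment | 30 | 20 | 10 |
| Control | 20 | 10 | 10 |
| Ohio total | 50 | 30 | 20 |
| Ratio | 1.5:1 | 2:1 | |

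To deliver 30 and 20 over two equal cohorts, each year would need 50/2 = 25 classrooms, split 15 and 10.

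**4. Do the focal children decide it?** Thirty focal children at one per classroom fit 30 Ohio classrooms. If every one of 50 Ohio classrooms had a focal child, the count would be 50. But 30 is also the stated number of treatment classrooms, so the match is suggestive and not decisive. The 495 children in section III.b do not help: 495/30 = 16.5 per classroom, but 495 is also 0.55 × 900, the stated share with disabilities applied to the stated number of children.

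**5. Does the total decide it?** The text does not say whether Kansas is within the 40.

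- 50 Ohio + 40 external (Kansas within) = 90
- 30 Ohio + 20 Kansas + 40 other external = 90
- 30 Ohio + 40 external (Kansas within) = 70

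Two of these readings reach 90, one from each Ohio allocation, so the total cannot choose between them.

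**The case against.** The strongest reply is that loose wording, and not two rival allocations, produced the mismatch. Take the 30 as every Ohio classroom that ever receives the intervention: 20 in fall plus 10 wait-list classrooms in spring. Take the 20 as the Kansas controls, and the 40 as other external sites. Then 30 + 20 + 40 = 90, and 30 focal children is one per Ohio classroom. Every count is accounted for.

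That reading is coherent as arithmetic and may be how the sentence arose, but the text does not say it. It needs the word Ohio to govern only the 30, assignment to treatment to include classrooms randomised to wait-list control, and the 40 to be called the remainder although the 20 are also external. Even if it is accepted, the randomised arms are still 20 and 10, so the introductory sentence still needs correcting.

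A second reply also has force: the randomisation sentence is explicit. A reader might infer that the randomised number per arm cannot be found in the plan. The documents do not support that. The described procedure gives 20 and 10; the fault is that the introductory sentence contradicts it.

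**Conclusion.** The point holds as an internal contradiction. The stated Ohio arms are each 10 classrooms larger than the described randomisation delivers: 30 and 20 against 20 and 10. This rests only on counts in section III.a and on taking the Ohio and OSU classrooms as the same set, which the text supports by saying that they are recruited across Ohio. The documents do not show which allocation is intended.

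Three stronger conclusions are tempting and should not be drawn.

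- **That the trial is underpowered, or loses a known amount of precision.** The plan states no power, effect size or standard deviation. Section III.g, Data Analysis, plans repeated-measures growth models with time-specific intervention status, so wait-list classrooms also contribute treated observations. A simple comparison of two arm sizes would match no planned analysis.
- **That the enrolment figures are overstated by a calculable amount.** The counts in section III.a already disagree (900 children, then about 770), so scaling them to a different number of classrooms would not be reliable.
- **That the total might be 110**, from 50 + 20 + 40. This contradicts the stated 90, and nothing in the text supports it.

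**What to change.** Reconcile the two statements in section III.a.

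- **If the described randomisation stands**, restate the Ohio allocation as 20 treatment and 10 wait-list control (30 classrooms, 30 focal children), and give 20 and 10 as the randomised number per arm. This costs text only, with no extra enrolment. The downside is that the stated randomised arms become smaller.
- **If 30 and 20 are intended**, correct the cohort size and yearly allocation (25 a year, split 15 and 10, if two equal cohorts are kept), and check the focal-child count, which would be 50 if every Ohio classroom has one. This is a real change: 50 − 30 = 20 more Ohio classrooms than the procedure provides.

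In either case, state whether the 20 Kansas classrooms are within the 40 external ones, and make the total of 90 agree. If there are 30 Ohio classrooms and Kansas is within the 40, the total becomes 70, and the teacher, child and parent counts given with it must be rechecked.

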#### **g. Data Analysis**

Aim 1 investigates the effects of peer-mediated PRT on the peer interactions and social status (indicated by individual centrality) within the classroom social network for children with LI. We assess this aim based on 6 to 24 repeated measurements for each outcome variable using multilevel growth models (Raudenbush & Bryk, 2002) to investigate changes in key outcomes over the school year and to accommodate the wait-list experimental design. Longitudinal measurements will be nested within participants and predicted by the time of measurement as well as time-specific intervention status. We include interaction terms between time of measurement and intervention status so that any accelerating or decelerating effects of intervention can be captured. In all models, we control for relevant covariates to increase precision of parameter estimates and power (Hox, Moerbeek, & Van de Schoot, 2010; Raudenbush, Martinez, & Spybrook, 2007). To assess treatment effects on peer interactions, we use the number of peer interaction, number of appropriate peer play, and duration of peer talk for the focal children as the outcome variables in the growth models. Depending on the distribution of the variables, appropriate linear or generalized linear models (e.g., Poisson) will be fitted. To examine treatment effects on social status, we compare the trajectories of individual centrality for the focal children and their classmates, controlling for classroom-level variation. Specifically, intervention effects are tested on key components of the trajectories, such as intercept, linear slope and quadratic slope (i.e., the slowing or acceleration of growth). The growth curves for different groups (treatment, wait-list control, and peer) can then be estimated. Aim 2 determines the extent to which peer-mediated PRT contributes to focal children's social, behavioral, and linguistic skills via the mediation of improved socialization experiences. For this aim, we employ multivariate latent growth models, where latent growth curves of socialization indices and child skills can be modelled simultaneously and the relationships between latent growth parameters examined. In particular, two latent slopes (fall and spring) will be specified for the socialization growth curve to capture the differential growth rate with and without intervention; intervention status will be used as a predictor of the two socialization slopes. Due to the sample size limitation, we will examine one socialization index and one skill variable at a time. We will focus on the following pathways: (a) effect of intervention on focal children's socialization experiences at fall, winter, and spring; and (b) effects of socialization experiences on child skills at fall, winter, and spring. Paths (a)\*(b) allow us to test the indirect effects of PRT on social, behavioral, and linguistic skills. To estimate the mediation effect, we use the product-of-coefficient approach (MacKinnon, Lockwood, Hoffman, West, & Sheets, 2002) with a bootstrapping procedure (Preacher & Hayes, 2004, 2008). This method does not require the assumption of normality for the sampling distribution of the product-of-coefficient. Finally, Aim 3 examines changes in classroom social network dynamics over the school year, and tests the effects of peer-mediated PRT on peer socialization at the classroom level. To address this aim,

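### Cohort year, within which the Ohio classrooms are randomised, is not named in the Aim 1 to 3 models; if outcomes differ between years, some standard errors will be modestly conservative

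*Combined protocol and SAP*

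**What the plan says.** Section III.a (Research Design) describes the Ohio recruitment thus: "Study methods with OSU classrooms use a sequential cohort design, with 15 classrooms participating in each of two consecutive years". Each fall has its own draw ("In the fall of each year, once all 15 classrooms are recruited, simple random assignment will be used"), in which "simple random assignment will be used to allocate 10 classrooms to the treatment group and 5 to the control group". Arm is therefore balanced on cohort by design, at 2:1 in both years.

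Section III.g (Data Analysis) sets out the Aim 1 model: "Longitudinal measurements will be nested within participants and predicted by the time of measurement as well as time-specific intervention status". It adds: "We include interaction terms between time of measurement and intervention status". It also promises unspecified relevant covariates and tests intervention effects on the intercept, linear slope and quadratic slope of the trajectories. Aim 2 uses intervention status to predict two latent slopes. Aim 3 repeats the Aim 1 approach with the classroom as the unit. The covariates listed under Descriptives and possible covariates (III.d) are classmates' language, classroom composition and focal-child sociodemographic factors. Cohort or year appears in none of these places.

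Section III.a also gives figures that do not fit two cohorts of 15. One sentence has the design "with 30 Ohio classrooms assigned to the treatment condition and 20 to the control condition", which makes 50 Ohio classrooms. For the external controls it says both "All remaining 40 classrooms will be recruited by our partners at external sites and serve control condition classrooms" and "We will thus incorporate 20 classrooms (University of Kansas) to serve as control condition classrooms".

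**The concern.** An analysis should normally condition on the factors within which randomisation was restricted. Because each year's draw is fixed at 10:5, a difference between years adds nothing to the true sampling error of the arm comparison. A model without cohort counts that difference as unexplained classroom variation and reports a standard error larger than the design delivers. What is at stake is some precision and power in a small trial, through wider intervals and tests that reject too rarely under the null. A false-positive risk is not at stake. Cohort is known for every classroom, so the loss is avoidable at little cost.

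**Working it through.** The documents state no alpha, power, effect size, SD, intraclass correlation or between-year difference. There is no planned figure to reproduce, and every size below rests on an assumed cohort gap d, in SDs of the quantity concerned between classrooms within a cohort.

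**1. Inputs from III.a.** 2 × 15 = 30 classrooms; treatment 2 × 10 = 20; control 2 × 5 = 10. Arm and cohort are orthogonal.

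**2. Variance absorbed when cohort is omitted.** With 15 classrooms per cohort, a gap d adds 30 × 0.25 × d² = 7.5d² to the residual sum of squares, spread over 28 degrees of freedom. Between-classroom variance is inflated by the factor 1 + 7.5d²/28: 1.067 at d = 0.5 and 1.268 at d = 1.0. The arm estimate is unchanged in expectation.

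**3. Time-specific intervention status.** Much of this effect is identified within classrooms, because status changes over the year, and a random intercept absorbs a level difference between cohorts. Generalised least-squares standard errors were computed with and without cohort, assuming 30 classrooms, 8 or 16 occasions, intraclass correlation 0.3 or 0.6, an untreated first occasion and a wait-list switch at mid-year:

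| d | SE overstated by |
|---|---|
| 0.2 | 0.0% |
| 0.5 | 0.0 to 0.2% |
| 1.0 | 0.0 to 0.7% |

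Varying when treatment starts and whether its status persists raises the maximum at d = 1.0 to 1.5%. A harsher version adds random slopes, a status-by-time term and a cohort gap in slope as well. Its maximum is 1.0%, 2.1% and 4.5% when cohort explains 5, 10 and 20% of the between-classroom variance (d about 0.46, 0.67 and 1.0).

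**4. Arm-by-time (slope) contrasts.** These compare slopes between classrooms, so a random intercept does not protect them. Scale the school year to run from 0 to 1, with equally spaced occasions. A classroom's estimated slope has variance τ² + σ²/S, where τ² is the slope variance, σ² the residual variance and S the sum of squared deviations of time. S = 0.857 for 8 occasions and 1.511 for 16. Let ρ = τ²/(τ² + σ²/S). Then

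SE without cohort terms ÷ SE with them = √(1 + ρ × 7.5d²/28).

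Take τ²/σ² from 0.5 to 2 (assumed):

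| Occasions | τ²/σ² | ρ | d = 0.5 | d = 1.0 |
|---|---|---|---|---|
| 8 | 0.5 | 0.300 | 1.010 | 1.039 |
| 8 | 2 | 0.632 | 1.021 | 1.081 |
| 16 | 0.5 | 0.430 | 1.014 | 1.056 |
| 16 | 2 | 0.751 | 1.025 | 1.096 |

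The overstatement is about 1 to 2% at d = 0.5 and about 4 to 9% at d = 1.0, with the most extreme setting at 2.5% and 9.6%.

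**5. Cost in degrees of freedom.** One cohort term takes a between-classroom contrast from 28 to 27 degrees of freedom, and the two-sided 5% critical value (level assumed) from 2.048 to 2.052.

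**6. Limit of the balance argument.** Suppose 20 external controls were pooled and all fell in year 2. The year-2 share would be 10/20 = 0.50 in the treatment arm and (5 + 20)/(10 + 20) = 0.83 among controls. Omitting cohort would then bias a simple arm difference by 0.33 of the cohort difference. With 40 external controls the control share is 45/50 = 0.90 and the bias 0.40. With an even split over years it is zero. The documents do not state their years.

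**The case against.** The strongest reply has four parts.

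- **The loss is conditional.** If two consecutive years have the same outcomes, it is zero, and the documents give no between-year difference. This stands; the point can only be put as a conditional.
- **Cohort is unnamed, not excluded.** The covariate clause is open and is meant to improve precision, and the list in III.d covers data to be collected, whereas cohort year is known by design. This stands as a matter of wording. An open clause still does not commit the analyst to the term.
- **The planned models already absorb most of the difference.** This stands for time-specific intervention status (step 3). It does not cover the intercept and slope comparisons that III.g also tests, or the slopes that Aim 2 regresses on intervention status (step 4).
- **Aim 2 has little room.** III.g itself limits Aim 2 to one index and one skill at a time because of sample size. Cohort paths to a socialization intercept, two socialization slopes and the skill growth parameters would be about five additional paths with 30 focal children. This stands and shapes the fix.

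A reader might also infer a larger loss from the textbook formula 1/√(1 − R²). With cohort explaining 5, 10 or 20% of between-classroom variance, it gives standard errors too large by 2.6, 5.4 or 11.8% and a true size of 4.5, 4.0 or 3.0% for a nominal 5% test. That arithmetic is correct for a single comparison of 20 with 10 classroom values. The plan does not describe that analysis, so these figures should not be attached to its growth models.

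**Conclusion.** The point holds as a minor matter of precision. Cohort is a randomisation stratum and no model names it. If years differ, the randomised comparison stays unbiased and its standard errors err on the large side: by under about 1% in most settings for the intervention-status effect, and by about 1 to 2% (slope gap 0.5 SD) to 4 to 9% (1.0 SD) for arm-by-time contrasts. The documents do not support the inferences that intervals will certainly be too wide or that the validity of the randomised comparison is threatened.

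The figures rest on the assumed gaps, variances and timings above and on 20 against 10 classrooms. The totals of 30 and 20 in III.a contradict that count and must be reconciled. The conclusion covers the randomised Ohio classrooms only. If non-randomised external controls are pooled, arm need not be balanced over years, and omission could bias the estimate. That is a separate question from the standard errors.

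**What to change.** In III.g, for Aims 1 and 3, state that cohort year and its interaction with time enter as fixed effects in the models for the randomised Ohio classrooms. This costs about one between-classroom degree of freedom per term.

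For Aim 2, state that cohort will be a predictor of the latent growth parameters only where the sample supports it. Say which parameters have priority, since the full set is about five more paths.

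In III.a, reconcile the Ohio totals (30 and 20 against 20 and 10) and the external totals (40 against 20), and give the years in which external classrooms take part. Any model that pools them needs its own handling of year and site; the randomised Ohio classrooms should also be analysed alone. These are text changes and need no new data collection from classrooms.
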